3.0 Inclusion and Exclusion Criteria

3.1 Describe the criteria that define who will be included or excluded in your final study sample.

Inclusion Criteria:

- (1) Identification by clinical care provider of new acute (defined by clinician as a symptom of recent origin developing with a time span of 48 hours) cognitive relapse or supratentorial GAD enhancing lesions on MRI with confirmation of cognitive decline.
 - (1a) Confirmation of cognitive decline will be obtained by administering the SDMT as a screening procedure for the study. Participants will qualify if they show a > -3 raw score point change on SDMT (relative to baseline identified to meet criteria #4).
- (2) Males/Females between the ages of 18-65 years who are capable of understanding and complying with the protocol, speak and write fluent English, and have at least a 9th grade education.
- (3) Have a diagnosis of Relapsing Remitting or early Secondary Progressive MS as per revised McDonald's Criteria.
- (4) Valid NP testing in the past 4-5 years
- (5) EDSS of ≤ 7.0
- (6) Have given written informed consent prior to any study-related procedure not part of normal medical care, with the understanding that consent may be withdrawn by the subject at any time without prejudice to his/her future medical care.
- (7) Are capable of performing the requirements of a NP test battery including at least 20/70 near visual acuity by near vision chart, with correction.

Exclusion Criteria:

- (1) Have cognitive deficits caused by concomitant medication usage or other significant neurological/psychological disease e.g. Alzheimer's disease, Parkinson's disease, stroke, transient ischemic attack, Vascular Dementia, Huntington's disease, traumatic brain injury, or chronic CNS infection.
- (2) Have evidence of any other medical cause(s) of cognitive impairment.

University at Buffalo Institutional Review Board (UBIRB)

Office of Research Compliance | Clinical and Translational Research Center Room 5018
[name]
UB Federalwide Assurance ID#: FWA00008824

PROTOCOL TITLE: Effects of adrenocorticotropic hormone (Acthar gel®) on recovery from cognitive relapses in MS.

- (3) Have evidence of current major depression as determined by a positive BDI-FS and clinician interview.
- (4) Clear new physical signs or symptoms that are referable to the spinal cord, brainstem, or optic nerve.
- (5) Evidence on MRI of new lesions in the brainstem, spinal cord, or optic nerve.

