- (6) Patients with changes to medications known to influence cognition (narcotics, stimulants, etc.) or to disease modifying therapy within one month of study initiation (or within a timeframe deemed high risk by treating physician) will be excluded.
- (7) Presence of current infections as determined by clinician interview.
- (8) Currently nursing, intentionally seeking pregnancy, or deemed at-risk for unplanned pregnancy.
- (9) Any concomitant medication, or medical condition contraindicated with Acthar.

3.2 Describe how individuals will be screened for eligibility.

All participants will undergo study eligibility screening and consenting by a Clinical Research Project Coordinator. The participants will be provided with a description of the required testing for study participation, and any risks will be described in order for the person to make an informed decision regarding voluntary study participation. This is also an opportunity for the person to ask questions regarding the study and the testing components. All study participants who choose to enroll in the study will be asked to sign and date the consent form in front of the Study Coordinator.

3.3 Indicate specifically whether you will include or exclude each of the following special populations: (You may not include members of these populations as subjects in your research unless you indicate this in your inclusion criteria.)

- Adults unable to consent
- Individuals who are not yet adults (infants, children, teenagers)
- Pregnant women
- Prisoners

University at Buffalo Institutional Review Board (UBIRB)

Office of Research Compliance | Clinical and Translational Research Center Room 5018
[name]
UB Federalwide Assurance ID#: FWA00008824

PROTOCOL TITLE: Effects of adrenocorticotropic hormone (Acthar gel®) on recovery from cognitive relapses in MS.

- Inclusion criteria state subjects must be willing and able to comply with study procedures for the duration of the study.
- Individuals under the age of 18 will not be included
- Pregnant women will not be included
- Prisoners will not be included

3.4 Indicate whether you will include non-English speaking individuals.

Provide justification if you will exclude non-English speaking individuals.

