9.0 Procedures Involved

University at Buffalo Institutional Review Board (UBIRB)

Office of Research Compliance | Clinical and Translational Research Center Room 5018
[name]
UB Federalwide Assurance ID#: FWA00008824

PROTOCOL TITLE: Effects of adrenocorticotropic hormone (Acthar gel®) on recovery from cognitive relapses in MS.

9.1 Describe and explain the study design.

9.2 Provide a description of all research procedures being performed and when they are performed, including procedures being performed to monitor subjects for safety or minimize risks.

Initial referral will be initiated by treating physicians. Following confirmation of the subject's relapse status and/or the presence of new supratentorial GAD enhancing lesions, patients deemed eligible for Acthar treatment will be screened for symptoms of infection and evaluated by their treating physician. If the patient agrees, the clinician will contact the research coordinator with the referral.

At this time, all participants will undergo study eligibility screening and consent by a Clinical Research Project Coordinator. The project coordinator or a designated member of the research team will meet, in person, with the participant to discuss the study objectives and procedures, so that he/she can make an informed decision regarding voluntary study participation. Participants will have an opportunity to ask questions regarding the study, procedures, etc. At this time, the study coordinator will administer the SDMT to the relapsing patient. The study coordinator will give this score to another study personnel. At this time the other

University at Buffalo Institutional Review Board (UBIRB)

Office of Research Compliance | Clinical and Translational Research Center Room 5018
[name]
UB Federalwide Assurance ID#: FWA00008824

PROTOCOL TITLE: Effects of adrenocorticotrophic hormone (Acthar gel®) on recovery from cognitive relapses in MS.

study personnel will check the patient's baseline SDMT score. If this score is less than or equal to a 3 point decline, the patient will be deemed eligible for the study. Participants who choose to enroll in the study will then be asked to sign and date a consent form in front of the Study Coordinator.

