As described above, enrolled subjects will complete the full cognitive baseline assessment [CVLT2 Learning → BVMTR Learning → SDMT → PASAT → DKEFS Sorting → CVLT2 Delayed Recall → BVMTR Delayed Recall → NAART]. Here the SDMT will be administered a second time to complete the run in for the information processing speed [IPS] composite. Participants will then be guided to complete other patient report questionnaires [BDIFS, FSS MSIS, MSNQ]. Finally, measures of motor function and clinical status will be assessed (EDSS and MSFC).

Acthar Gel will then be administered by a research coordinator to the relapsing patient in accordance with the recommendations set forth in the package insert. The dosage may be individualized according to the medical condition of each patient. Frequency and dose of the drug may be determined by considering the severity of the disease and the initial response of the patient. Acthar will be provided through the study.

As cognitive relapses are typically milder (compared to physically focused relapses) subjects will be initially dosed for 5 days and pending clinical response or adverse events treatment may be continued for the full 2 weeks in the opinion of the investigator. At study enrollment participants will be instructed on self-administration procedure and supplied with a 5-day course of Acthar® Gel (5ml/80 IU). Medication will be administered through either subcutaneous or intramuscular self-injection (selected by the patient). Patients will be instructed by trained clinical staff on self-administration and will self-administer the first injection under observation in the clinic.

The neuropsychological evaluation takes approximately 45 minutes to complete. The neurological exam takes about 15 minutes. Training and administration of the drug takes about 15 minutes. The neuropsychological assessment will be repeated at 90 days. All participants will be given \$200 at the completion of the study. At the time of consenting, each participant will complete a W-9 form. Checks will be mailed from our billing department directly to the participant's address of choice.

The treating neurologist will be responsible for identifying patients agreeing to treatment with the study drug and for insuring that the EDSS is

University at Buffalo Institutional Review Board (UBIRB)

Office of Research Compliance | Clinical and Translational Research Center Room 5018
[name]
UB Federalwide Assurance ID#: FWA00008824

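### The visible protocol requires no pregnancy test before the first Acthar injection, although women of childbearing potential may enrol and the fetal effect is called unknown

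*Combined protocol and SAP*

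**What the plan says.** Section 3.1, inclusion criterion 2, admits "Males/Females between the ages of 18-65 years". Section 3.3 states "Pregnant women will not be included", and exclusion criterion 8 removes anyone "Currently nursing, intentionally seeking pregnancy, or deemed at-risk for unplanned pregnancy". Exclusion criterion 9 removes patients with "Any concomitant medication, or medical condition contraindicated with Acthar".

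The prompt for section 9.2 asks for a description of all research procedures, "including procedures being performed to monitor subjects for safety or minimize risks". The answer begins with referral, at which "patients deemed eligible for Acthar treatment will be screened for symptoms of infection and evaluated by their treating physician". It then describes the screening SDMT, consent, the cognitive battery, the questionnaires, and the EDSS and MSFC. Acthar follows, given "in accordance with the recommendations set forth in the package insert", with the first self-injection observed in clinic. The same section says that a detailed clinical assessment comes before enrolment, but does not say what it contains.

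Section 14.1 tells women of childbearing potential not to become pregnant during the study. It describes the fetal effect as unknown, warns that continuing the drug may be unsafe, and asks for immediate reporting followed by removal from the study. Section 9.3 has the site report any pregnancy and follow it to its outcome.

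**The concern.** Pregnancy is a stated bar to entry, but the visible text gives the coordinator who screens for eligibility no means of confirming that it is absent. Exclusion criterion 8 rests on a judgement and names no assessor, test or contraception standard. Exclusion criterion 7, by contrast, does state a method for infection: "Presence of current infections as determined by clinician interview".

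What is at stake is the safety of the participant and a fetus, not the validity of the results. A woman judged not at risk may be pregnant without knowing it. On the plan as written she would be dosed with a drug whose fetal effect the protocol itself calls unknown.

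**Working it through.** No statistical formula applies, and the protocol gives no figure to reproduce. The check is a reading of every section that could hold a pregnancy test, followed by simple counts.

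**Can women of childbearing potential enrol?** Inclusion criterion 2 covers both sexes from 18 to 65 years, and section 14.1 addresses such women as participants. The protocol does not state it outright, but the two sections together imply it.

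**Is a test among the listed procedures?**

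- Section 9.2, day-0 entries: CVLT2 learning, BVMTR learning, SDMT, PASAT, DKEFS Sorting, CVLT2 delayed, BVMTR delayed, NAART, BDIFS, FSS, MSIS, MSNQ, EDSS, MSFC. That is 14 entries, or 14 − 2 = 12 distinct instruments, because CVLT2 and BVMTR each appear twice. Pregnancy tests: 0.
- Section 9.5, source records: EDSS, SDMT, PASAT, CVLT2, BVMT-R, MSFC, BDIFS, FSS, MSIS, MSNQ, NAART. That is 11 entries. Pregnancy tests: 0.
- Steps before day-0 testing in section 9.2: an infection-symptom check, a physician evaluation of unstated content, the screening SDMT and consent. No test is named.

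The lists are not exhaustive. Section 9.5, for example, omits DKEFS Sorting and adverse-event records. The counts therefore show that no test is specified, not that none is performed.

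**Would a later provision catch an unrecognised pregnancy in time?**

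- The initial course lasts 5 days (section 9.2).
- The first scheduled safety contact is on day 7 (sections 9.2, 9.3 and 12.1). In section 9.2 it covers concomitant medications and adverse events; pregnancy is not named.
- Since 5 < 7, the initial course is normally over before that contact. Only a course extended towards two weeks would still be running.
- The reporting rules in sections 9.3 and 14.1, and the 24/7 telephone in section 14.2, depend on the patient already knowing or suspecting that she is pregnant.

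**Size of the remedy.** Only the 30 Acthar patients are dosed, so between 0 and 30 tests are needed, depending on how many are women of childbearing potential. A woman who tests positive and is replaced may add one more. The stated day-0 components take 45 + 15 + 15 = 75 minutes, not counting consent or the screening SDMT. Assuming 5 to 10 minutes per test (not a protocol figure), the visit lengthens by 5/75 = 6.7% to 10/75 = 13.3% if the test is done in sequence, or by almost nothing if it runs during the 45-minute battery.

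The number of women of childbearing potential and the frequency of unrecognised pregnancy cannot be derived from the documents, so no risk figure is given.

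**The case against.** The strongest reply is that the protocol already excludes pregnancy and goes further by excluding women at risk of an unplanned one. A physician evaluates each patient, a clinical assessment precedes enrolment, contraindicated conditions are excluded, and dosing follows the package insert. A test may be part of any of these, or may be set out in the figure just before section 9, the consent pages or Appendix 1, none of which is available here. Section 9.1 has no text answer, so that figure could be the study design or visit schedule. The procedure lists are mainly neuropsychological, and they also omit checks that the protocol does require, such as near visual acuity. The comparison with exclusion criterion 7 is limited too: that criterion names an interview rather than a laboratory test, and several other exclusions name no method.

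Much of this stands. The gap is one of objective verification, not of exclusion, and the counts alone are weak evidence. What does not follow is that the gap is closed. No visible text supplies a test, and section 9.2 is where the form asks for procedures that reduce risk. A judgement about the risk of becoming pregnant is also not a check on whether a patient is pregnant now.

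**Conclusion.** The concern holds for the visible protocol: no pregnancy test is specified before dosing, and the remaining safeguards start only when a pregnancy is known. It is a minor point, worth acting on because the remedy is cheap. Sample size, power and the efficacy analysis are unaffected.

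The conclusion rests on two assumptions: that women of childbearing potential do enrol, and that no test is required in the unseen figure, consent pages or Appendix 1, under the package insert, or within the clinical assessment. If one is, only the missing cross-reference remains. Confidence is medium for that reason.

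**What to change.** Add a sentence to section 9.2 requiring a documented negative pregnancy test in women of childbearing potential at the day-0 visit, before the observed first injection. Keep exclusion criterion 8 and the reporting rule in section 14.1, because a very early pregnancy can still test negative. It would also help to say who makes the at-risk judgement and against what contraception standard. If a test is already required elsewhere, a cross-reference in section 9.2 is sufficient.

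The cost is a short amendment, about 30 tests at most, a few minutes per patient and a small test charge, all at a visit that already takes place in clinic. A positive result would need confidential handling.

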4.0 Study-Wide Number of Subjects (Multisite/Multicenter Only)

4.1 If this is a multicenter study, indicate the total number of subjects to be accrued across all sites.

N/A

5.0 Study-Wide Recruitment Methods (Multisite/Multicenter Only)

If this is a multicenter study and subjects will be recruited by methods not under the control of the local site (e.g., call centers, national advertisements) describe those methods. Local recruitment methods are described later in the protocol.

5.1 Describe when, where, and how potential subjects will be recruited.

University at Buffalo Institutional Review Board (UBIRB)

Office of Research Compliance | Clinical and Translational Research Center Room 5018
[name]
UB Federalwide Assurance ID#: FWA00008824

PROTOCOL TITLE: Effects of adrenocorticotropic hormone (Acthar gel®) on recovery from cognitive relapses in MS.

N/A

5.2 Describe the methods that will be used to identify potential subjects.

N/A

5.3 Describe materials that will be used to recruit subjects. (Attach copies of these documents with the application. For advertisements, attach the final copy of printed advertisements. When advertisements are taped for broadcast, attach the final audio/video tape. You may submit the wording of the advertisement prior to taping to preclude re-taping because of inappropriate wording, provided the IRB reviews the final audio/video tape.)

N/A

6.0 Multi-Site Research (Multisite/Multicenter Only)

6.1 If this is a multi-site study where you are the lead investigator, describe the processes to ensure communication among sites, such as:

- All sites have the most current version of the protocol, consent document, and HIPAA authorization.*
- All required approvals have been obtained at each site (including approval by the site's IRB of record).*
- All modifications have been communicated to sites, and approved (including approval by the site's IRB of record) before the modification is implemented.*
- All engaged participating sites will safeguard data as required by local information security policies.*
- All local site investigators conduct the study appropriately.*
- All non-compliance with the study protocol or applicable requirements will be reported in accordance with local policy.*

N/A

6.2 Describe the method for communicating to engaged participating sites:

University at Buffalo Institutional Review Board (UBIRB)

Office of Research Compliance | Clinical and Translational Research Center Room 5018
[name]
UB Federalwide Assurance ID#: FWA00008824

PROTOCOL TITLE: Effects of adrenocorticotropic hormone (Acthar gel®) on recovery from cognitive relapses in MS.

- *Problems.*
- *Interim results.*
- *The closure of a study*

N/A

7.0 Study Timelines

7.1 *Describe the duration of an individual subject's participation in the study.*

This is a prospective, open-label study of Acthar administered as treatment for an acute cognitive relapse. Primary and secondary endpoints will be collected prior to Acthar administration and at 3-month follow-up. Comparison will be made to a stable MS control group.

7.2 *Describe the duration anticipated to enroll all study subjects.*

Enrollment of all study participants is expected to take 4 years (48 months).

7.3 *Describe the estimated date for the investigators to complete this study (complete primary analyses)*

Completion of this study, including primary analysis, is expected within 5 years.

8.0 Study Endpoints

8.1 *Describe the primary and secondary study endpoints.*

Primary measures will include: Symbol Digit Modalities Test,¹⁴ Brief Visualspatial Memory Test- Revised,¹⁵ Paced Auditory Serial Addition Test,¹⁶ and the Multiple Sclerosis Functional Composite (MSFC).²³ These tests are some of the strongest indicators of clinically relevant cognitive change available in MS.

The Symbol Digit Modalities Test (SDMT) will be used to measure visual processing speed. This test presents a stimulus key of numbers paired with abstract symbols at the top of a page. Participants scan the page below the key which has rows of symbols without the paired numbers. The task is to generate the associated numbers orally as fast as possible. We will employ the Rao oral adaptation²⁴ of the SDMT as the oral presentation has been deemed most appropriate for use with a potentially motor impaired population.¹²

University at Buffalo Institutional Review Board (UBIRB)

Office of Research Compliance | Clinical and Translational Research Center Room 5018
[name]
UB Federalwide Assurance ID#: FWA00008824

PROTOCOL TITLE: Effects of adrenocorticotropic hormone (Acthar gel®) on recovery from cognitive relapses in MS.

The Paced Auditory Serial Addition Test (PASAT)²⁵ 3 sec interval version will be used as an indicator of working memory performance. The PASAT is an auditory task in which subjects are exposed to single digit numbers voiced every three seconds. After each number presentation, the subject's task is to respond with the sum of the last two digits presented. As each new number is presented, the subject must recall the previous digit, add them together, and respond before the next number is presented.

The Multiple Sclerosis Functional Composite (MSFC)²³ is a composite measure incorporating aspects of cognition, walking speed and manual dexterity. The 25-foot walk, 9-hole peg test, and PASAT 3-sec (described above) are normalized based on an established normative sample and an overall composite z- score is then determined. This composite is frequently used as a primary outcome in clinical trials as it covers three major domains of function potentially impaired in MS.

The Brief Visuospatial Memory Test Revised (BVMTR)^{26,27} is a measure of episodic memory. This task presents a display of six visual designs presented on an 8.5 x 11 piece of paper for three consecutive learning trials. During each trial the stimulus is presented for 10 seconds, after which the participant is asked to draw the figures as accurately as possible in their correct locations. The six designs receive a score of 0, 1, or 2 based on accuracy and location. After a 20-25 minute delay, participants are again asked to recall and draw the designs.

The North American Adult Reading Test (NAART) is a measure of verbal ability. Patients are asked to read a list of words aloud.

Secondary measures will include: self and informant ratings of cognitive problems using the Multiple Sclerosis Neuropsychological Questionnaire,²⁸ the Expanded Disability Status Scale,²⁹ the Multiple Sclerosis Impact Scale, the Beck Depression Inventory – Fast Screen, and subscales from the Sickness Impact Profile³⁰ (an assessment of health related quality of life and activities of daily living). Incidence of adverse events and concurrent medications will also be recorded as potential covariates.

8.2 Describe any primary or secondary safety endpoints.

N/A

[figure not shown]
